1. SELECTION OF PATIENTS

Patients in this study will have chronic stroke-induced aphasia. Diagnostic evaluations will be conducted during the patients' initial visit to confirm aphasia diagnosis. Patients currently receiving speech and language treatment (apart from aphasia support groups) will be required to temporarily discontinue involvement until study completion.

1.1 Patient Inclusion Criteria

Patients must satisfy the following inclusion criteria to be considered eligible for entry into this study:

1. Patients must be willing and able to give informed consent.*
2. Patients must be willing and able to comply with study requirements.
3. Patients must be between 25- and 80-years of age.
4. Patients must be native English speakers.
5. Patients must be pre-morbidly right-handed.
6. Patients must have sustained a one-time ischemic stroke in the left-hemisphere.
7. Patients must be greater than 6-months post-stroke.
8. Patients must have an aphasia diagnosis as confirmed by the *Western Aphasia Battery-Revised*.
9. Patients must be MRI-compatible (e.g., no metal implants, not claustrophobic, etc.).
10. Patients must achieve at least 65% accuracy on naming task during screening.

1.2 Patient Exclusion Criteria

Patients with any of the following characteristics will not be eligible for entry into this study:

1. History of brain surgery
2. Seizures during the previous 12 months
3. Use of medications that lower the seizure threshold (e.g., Ritalin, Adderall, Bupropion, etc.)
4. Sensitive scalp (per patient report)
5. Able to overtly name more than an average of 140 out of 175 items during the pre-treatment picture naming test (Philadelphia Naming Test) during Visits 2 or 3
6. Unable to overtly name at least a total of 5 out of 160 items during the pre-treatment fMRI sessions during Visits 2 or 3

*The investigators in charge of this study are speech-language pathologists who have expertise in assessing, treating, consenting, and communicating with adults with speech-language impairment of many types and severities. It is important to note that aphasia is an impairment of speech-language, not intelligence, and that most often, in the absence of comorbid impairment(s), competence is not reduced but only masked by the speech-language impairment. The consent document is reviewed thoroughly, with verification questions asked frequently to ensure that the potential participant and his or her caregiver understand the scope of the research project. Only participants who clearly understand the research and are able to indicate consent to participate can be enrolled in this study. Caretakers, family, or friends must be present during consent approval, but they cannot consent for the participant. If written consent is not possible, they may act as witnesses for verbal consent. Crucially, because this population is not devoid of language and can make their wants, needs, and preferences known (either via impaired speech or via alternative communication modalities such as gestures, writing, etc.), participants who have the ability to consent also have the ability to inform the investigators that they wish to cease their participation if necessary.

2. STUDY PROCEDURES

2.1 Study Procedures Overview

After informed consent is received, a neurological examination will be performed and multiple screening assessments will be conducted including a tDCS and MRI safety screening (see below). If the patient passes the initial screening portion, speech and language diagnostic testing will be conducted during the same visit (Visit 1). During the next two visits (Visits 2 and 3), patients will undergo baseline assessments of naming ability and connected speech, and structural and functional MRI examinations. The fourth visit will include collection of blood sample, electrode positioning and tDCS treatment administration. Patients will receive 15 sessions (Visits 4-18) of tDCS treatment administration. At the beginning of Visit 4, eligible patients will be randomized to receive either A-tDCS (1 mA) or S-tDCS (placebo) for 15 consecutive weekdays (20-min per each 45-min behavioral treatment session). A computerized anomia treatment will be coupled with the stimulation. The computerized treatment task will be 45-minutes in total length, so that it will commence at the same time as the tDCS administration and continue for another 25-minutes after the tDCS has ceased. To assess cardiovascular arousal, blood pressure and heart rate will be measured before and after each session. Additionally, discomfort ratings will be recorded following the end of each session using the *Wong-Baker FACES Pain Rating Scale* and a weekly neurological exam will be administered by a neurologist. Utilizing a computerized picture naming assessment (which combines the 175 items from the PNT and 80 treated items) of trained and untrained nouns, all patients will be assessed at 8 different time points throughout the experiment: twice at baseline (Visit 2 and 3), twice immediately following the fifteenth (and final) treatment session (Visit 19 and Visit 20), twice at 4 weeks follow-up (Visit 21 and Visit 22), and twice at 6 months follow-up (Visit 23 and Visit 24).

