2.2.6 Procedures for Electrode Positioning (Visit 4)

The following procedures will be performed:

1. Fit the patient with a latex scalp cap and instruct them to sit as still as possible during this process
2. Identify and label the following six anatomical landmarks on the patient's scalp cap utilizing a permanent marker: 1) left ear; 2) right ear; 3) left eyebrow; 4) right eyebrow; 5) head apex; and 6) occipital bun
3. Upload the patient's anatomical T1 MRI scan (acquired from Visit 2) onto a computer utilizing *MRicro*, a computer program that allows for the viewing of MRI images.
4. Employing *MRicro*, select an anatomical location on the patient's T1 MRI scan (e.g., bridge of nose) by mouse-click
5. Move the magnet sensor from the *Flock of Birds* magnetic tracking system to the location on the patient's head which mirrors the anatomical position selected in *MRicro* from Step 4 and enter into the *MRireg* software, a computer program that registers a high-resolution MRI scan of the head with scalp locations
6. Repeat Steps 4 and 5 until the following five anatomical landmarks have been entered into *MRireg*: 1) left ear; 2) right ear; 3) bridge of nose; 4) head apex; and 5) occipital bun
7. Press the 'correlation line' button of *MRireg* after the five anatomical landmarks from Step 6 have been located
8. Enter the coordinates of the area of the left hemisphere with the highest level of activation within the peri-lesional area during correct naming on the fMRI naming task in the 'desired MRI' boxes (these coordinates will be identified by Dr. [name] and forwarded to you [SLP] on patient-by-patient basis)
9. *MRireg* will estimate the current distance of the magnet sensor wand from this point. Move the wand around the patient's head and once the most precise area is located, label the location on the patient's scalp cap with a star utilizing a permanent marker

Below: Example of Step 4

Left: Example of Steps 8 & 9. The 'desired MRI boxes' are displayed. Additionally, the current distance of the magnetic sensor from the coordinates entered in the 'desired MRI boxes' is displayed, which in this example, is 30.9 mm.

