2.2.7 Procedures for Collection of Blood sample (Visit 4)

1. Collection of blood samples will be handled by the study coordinators (both are registered nurses) assisting Drs. [name] and [name]
2. Once blood sample has been obtained, write patient number (as generated by the DCU) on the vial
3. Follow storage procedures as advised by [name] lab at MUSC
4. At USC, place the blood sample in the lab freezer in [name] lab
5. At MUSC, place the blood sample in the designated lab freezer in [name] lab

[figure not shown]

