2.2.8 Procedures for Treatment (Visits 4-18)

The following procedures will be performed:

1. Measure and record the patient's blood pressure and heart rate
2. Carefully fit patients with their scalp cap (labeled from Visit 4)
3. Soak the 2 sponge electrodes in saline solution and place inside rubber electrode holders
4. Place the anode electrode under the designated area on the scalp cap that was located during the electrode positioning process (marked with a star during Visit 4). Remove the cap and secure electrode placement with a self-adhesive bandage
5. Place the reference cathode electrode on the patient's right orbito-frontal scalp (above the right eyebrow) and secure electrode placement with a self-adhesive bandage
6. Connect the electrode cables to the relay box positioned between the tDCS stimulator and the lap-top computer used to maintain experimenter and patient blinding. Start the software used for blinding (see an icon "tDCS+aphasia" on the desktop) and enter the patient number (obtained on the DCU web site) in the designated place. Make sure that the screen of the "blinding" lap-top is placed out of patients' sight.
7. Turn on tDCS stimulator
8. Set-up the computerized anomia task:
 - o Turn on computer and position in front of patient
 - o Plug in the red/green response buttons into the computer and position in front of patient
 - o Plug in the earbud headphones into the computer and place in patient's ears

- Play example sound clip to verify with patient that sound is sufficient; if sound is not sufficient, adjust volume until patient is satisfied
 - Locate the patient's designated treatment folder and open
9. Instruct the patient how to perform the self-administered computerized anomia treatment consisting of a picture-word matching task, which will be coupled with the stimulation
- The computerized treatment task will be 45-minutes in total length, so that it will commence at the same time as the tDCS administration

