 - A picture will be presented for 2 s on a laptop computer screen and will be immediately followed by an audio-visual display of a male speaker's mouth saying a noun. Video of the speaker producing the noun is presented in synchrony with the audio via in-ear headphones. The spoken word either will or will not match the preceding picture. In the event of a match, instruct the patient to press a large green response button interfaced with the computer, and in the case of a non-match, instruct the patient to press a red button. Half of the picture/word pairs will match, while the other half will not. The computer will provide immediate visual feedback following a response in the form of a "smiley face" for correct answers and a "frowny face" for incorrect answers. Additionally, following the completion of a treatment session, a data file of the patient's responses will be automatically saved, and the accuracy score from that session will be displayed on the computer screen.

Right: Example of the computerized treatment task. The picture representation for "cat" does not match the subsequent audio-visual presentation for "leg." Since the pair is not a match, the red button was correctly pressed, which lead to the immediate "smiley face" feedback.

10. "Click" on the START icon on the "blinding" computer to simultaneously start stimulation and the computer treatment task
11. Measure and record the patient's blood pressure and heart rate following treatment completion
12. Record any Adverse Events experienced during the treatment session or since the last visit on the AE log.
13. Assess and record the patient's comfort rating using the *Wong-Baker FACES Pain Rating Scale* following treatment completion

Left: A reproduction of the "Wong-Baker FACES Pain Rating Scale"

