3. STATISTICAL CONSIDERATIONS FOR THE PRIMARY STUDY AIM

3.1 Analysis Sample

The primary analysis will be analyzed under the intent-to-treat principle (ITT). Under this principle, the evaluable sample will include all participants who are randomized regardless of the type of treatment that was actually administered. For the safety analyses, all randomized participants who receive at least one session of the treatment will be included, regardless of the duration of treatment administered.

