A “Real-Time” randomization procedure is implemented via the Trial Website on the WebDCU™ System where the clinical center staff enters the basic baseline (e.g. aphasia type, and AQ severity) and eligibility information of a subject prior to enrollment. If the subject’s eligibility status is confirmed, the computer program on the WebDCU™ server will evaluate the treatment arm distribution and generate a patient number based on the randomization scheme. The SLP enrolling the patient will not see the treatment assignment, only a numeric patient number which is entered into a software package that controls whether the tDCS given is A-tDCS or S-tDCS. In order to mask treatment type (A-tDCS vs. S-tDCS) for both patients as well as the SLPs administering the treatment session (ie. setting up the tDCS and starting and monitoring the computerized treatment task), we use in-house software/hardware. As previously discussed, this setup allows for switching the tDCS on and off without any involvement from the patient or experimenter. The software is run on a lap-top computer connected to the tDCS stimulator. Treatment type is encoded in the software so that the administrator only needs to enter a patient and session number to start stimulation without knowing whether those specific numbers are

associated with A-tDCS or S-tDCS. The unblinded list of randomization codes and treatment assignments will be generated by the DCU and will be uploaded into the software by a software administrator who is not otherwise involved in the study.

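### Randomisation at the start of Visit 4 comes before the blood draw, electrode positioning and first vital signs, so a patient who stops there is in the intent-to-treat set without having been stimulated.

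*Protocol*

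**What the plan says.** Protocol 2.1 sets the time of assignment ("At the beginning of Visit 4, eligible patients will be randomized") and lists what else happens that day: "The fourth visit will include collection of blood sample, electrode positioning and tDCS treatment administration".

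Other sections confirm that assignment comes first. Under Protocol 3.2, once eligibility is confirmed the WebDCU program will "generate a patient number based on the randomization scheme". Under Protocol 2.2.7, staff "write patient number (as generated by the DCU) on the vial", so the number is expected to exist when the sample is labelled. Positioning (Protocol 2.2.6) begins with this instruction: "Fit the patient with a latex scalp cap and instruct them to sit as still as possible during this process". The treatment procedure (Protocol 2.2.8) opens with "Measure and record the patient's blood pressure and heart rate". The patient number goes into the blinding software at step 6, and only at step 10 does the clinician click START "to simultaneously start stimulation and the computer treatment task".

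Protocol 3.1 defines the primary set: "the evaluable sample will include all participants who are randomized regardless of the type of treatment that was actually administered". SAP 5.2 likewise includes everyone randomised. Missing primary outcomes are multiply imputed under a missing-at-random assumption (Protocol 3.4.5, SAP 8.5).

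**The concern.** Positioning uses the MRI scan and the fMRI coordinates. The blood draw and vital signs are the same in both arms. The assignment has no use until the patient number reaches the blinding software, yet it is made before all of these steps. Visit 4 is also the first time the documents describe a cap fitting or a blood draw, so it is a natural point for a patient to find the procedure unwelcome.

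The direction matters because of the futility design. The null hypothesis is that active exceeds sham by at least 1.5 points, and rejecting it ends development. Measured active patients who were never stimulated shrink the observed difference and push toward rejection. If they are not measured, their outcomes must be imputed, and neither document states which variables the imputation model uses. A later randomisation within the same visit would avoid either consequence for patients who stop at these steps.

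**Working it through.** **Inputs from the documents.** Margin 1.5 points (Protocol 3.4.2, SAP 8.2). SD 2.6, one-sided alpha 0.10, 85% power, 33 per arm raised to 37 for 5% drop-out, and mean changes of 4 (sham) and 5.5 (active at the margin) (Protocol 3.4.3, SAP 8.3).

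**Assumptions.** The number k of never-stimulated active patients and their mean change are not in the documents.

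**1. The plan's own figures.**
- n per arm = 2 × 2.6² × (1.2816 + 1.0364)² / 1.5² = 32.3, rounded up to 33.
- Power at 33: SE = 2.6 × √(2/33) = 0.640, and Φ(1.5/0.640 − 1.2816) = 0.856 (0.852 with the noncentral t).
- Inflation: 33/0.95² = 36.6, rounded up to 37. Simple replacement, 33/0.95 = 34.7, would give 35.

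The stated figures reproduce and are not in dispute.

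**2. Never stimulated and outcome missing.** One patient is 1/37 = 2.7% of an arm, and uses one of the 37 − 33 = 4 places added for drop-out. The outcome is imputed. If the model uses assigned arm, the cost is mainly precision, and the dilution in step 3 does not follow.

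**3. Never stimulated but measured, active arm only, sham-like change.** With k such patients the intent-to-treat difference is 1.5 × (1 − k/37). SE = 2.6 × √(2/37) = 0.604. The probability of declaring futility is Φ(1.5 × (k/37)/0.604 − 1.2816).

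| k | Difference | Normal approximation | Noncentral t |
|---|---|---|---|
| 0 | 1.500 | 10.0% | 10.0% |
| 1 | 1.459 | 11.2% | 11.2% |
| 2 | 1.419 | 12.6% | 12.5% |
| 3 | 1.378 | 14.0% | 14.0% |

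**4. Sensitivity to the sham-like change.** Someone who leaves at Visit 4 also misses the computerised naming treatment, which sham patients receive, so a sham-like change may be too favourable. As a range for one patient, take a mean change of 4 (sham-like) down to 0 (none), with the SD held at 2.6.
- Active loss only: difference (36 × 5.5 + 4)/37 − 4 = 1.459 to (36 × 5.5 + 0)/37 − 4 = 1.351. Probability 11.2% to 15.0%.
- Sham loss only: difference 5.5 − (36 × 4 + 4)/37 = 1.500 to 5.5 − (36 × 4 + 0)/37 = 1.608. Probability 10.0% to 7.2%.
- One loss in each arm with the same mean change: that change cancels, leaving 1.5 × 36/37 = 1.459 and 11.2%.

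**The case against.** The strongest reply is that the documents show no route by which many patients would be lost here. None of the Visit 4 steps has a pass/fail rule. Blood pressure and heart rate are recorded to assess arousal, with no threshold. Nothing makes treatment depend on giving blood. Sensitive scalp, tDCS and MRI safety, and naming ability are all screened at Visits 1 to 3, and randomising on the day of first treatment already keeps the gap short. All of this stands, and it is why the expected number is small. A reader might infer that patients will fail these steps; the documents support only withdrawal or intolerance as the route.

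Second, the steps are blinded and independent of arm, so losses should balance in expectation, and few patients who leave at Visit 4 would return for Visits 19 and 20. This also stands. The table in step 3 is conditional on active-arm patients who do return, and is not a forecast. Balance alone does not remove the dilution, as the last line of step 4 shows.

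Third, it is tempting to call the increase above 10% an inflated type I error. The hypothesis concerns the expected change by arm, analysed by intent to treat. If unstimulated patients bring that true difference below 1.5, the null hypothesis as written is false, and rejecting it is not a type I error. The increase is relative only to a benefit of 1.5 among treated patients.

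Fourth, the plan already has a drop-out allowance, a safety set requiring at least one session (SAP 5.3) and a per-protocol analysis requiring 80% of sessions (SAP 5.4). The allowance protects power but does not counter dilution, and the per-protocol analysis is secondary, so neither repairs the primary test.

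Last, this is not an argument against intent to treat. Nobody would be removed after randomisation.

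**Conclusion.** The point holds as a minor, inexpensive improvement. The sequence is clear from the documents: assignment comes first, three steps that do not need it follow, and everyone assigned is analysed. Avoidable never-stimulated patients can therefore enter the primary set.

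The size is modest and conditional. Each loss is one of 37 outcomes in an arm. One measured never-stimulated active patient moves the probability of declaring futility from 10.0% to about 11.2% at a treated-patient benefit of 1.5, assuming a sham-like change, SD 2.6 and no matching sham loss. How many such patients to expect is not in the documents; with screening complete before Visit 4, it is likely few or none. The documents do not support any claim that the futility test is materially compromised.

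**What to change.** Amend Protocol 2.1, 2.2.6, 2.2.7 and 2.2.8 so that the Visit 4 order is:

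1. Confirm eligibility.
2. Complete electrode positioning, pre-session blood pressure and heart rate, and device and task set-up.
3. Randomise in WebDCU immediately before the patient number is entered in the blinding software.
4. Enter the number and start.

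Set-up has to move as well: number entry is now step 6 and START is step 10, so moving randomisation to just before step 6 without moving set-up would still leave switching on the stimulator, task set-up and patient instruction after assignment.

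For the blood sample, either draw it beforehand and write the patient number on the vial once it is generated in the same visit, or draw it after randomisation. The first option removes one more point of loss but needs a brief labelling or linkage step, because the temporary number in Protocol 2.2.1 is issued only for initial screening. The second leaves the draw as a post-randomisation step.

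The cost is a small reordering and that labelling step, with no new procedure, visit or sample-size change. Drop-out after the first session is unaffected.

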2.2.1 Procedures for Screening (Visit 1)

The following procedures will be performed:

1. Obtain written informed consent:
 - A signed and dated informed consent form will be obtained from each patient before conducting any screening procedures. Patients will be then be assigned a temporary identification number for the purposes of initial screening.
 - All research staff authorized to obtain informed consent will have completed the Miami CITI course in the Responsible Conduct of Research and Protection of Human Subjects prior to their involvement with the study. Furthermore, they will be oriented to the study and trained by the study PI and study co-investigators who have all had extensive training and experience in the ethical and practical aspects of informed consent procedures.
2. Review inclusion/exclusion criteria
3. Obtain medical history
4. Conduct neurological examination
5. Administer the A-tDCS safety screening
6. Administer the MRI safety screening
7. Administer naming screen used to verify that patients comprehend task requirements

o Refer to computer setup for the treatment for information regarding the computerized naming assessment. A shortened naming screen (identical set up and response requirements) will be presented to patients. Patients will get three attempts to achieve at least 65% accuracy on the task. If a patient is unable to reach this level of accuracy, study enrollment will be discontinued.

2.2.2 Procedures for Diagnostic Testing (Visit 1)

If the patient passes the screening portion, diagnostic testing will be conducted during the same visit. The following diagnostic testing procedures will be performed:

1. Administer the *Western Aphasia Battery-Revised* (WAB-R):
 - o The WAB-R will characterize the patients' overall language impairment through the evaluation of the main clinical aspects of language functioning, including speech content, speech fluency, auditory comprehension, repetition, and naming. The WAB-R allows for the differentiation of these specific language abilities, as well as the classification of aphasia type. The WAB-R also yields a composite score, the Aphasia Quotient, which provides an overall measure of severity, in which lower scores denote more severe aphasia (Kertesz, 2007). Speech-language pathologists (SLPs) will refer to the manual for explicit instructions regarding administration and scoring procedures. Administration time will range between 30-45 minutes.
2. Administer the *Boston Naming Test-Second Edition* (BNT):
 - o The BNT represents a measure of object naming abilities from a corpus of 60 line drawings. Object names are ranked along a continuum, with easier, more higher-frequency words appearing at the beginning of the test and more difficult, lower-frequency words appearing near the end. To eliminate patient frustration, the BNT implements a ceiling effect so that once the patient incorrectly names eight items in a row, testing will cease, with the assumption that (s)he would not correctly name the upcoming, more difficult words (Kaplan, Goodglass, & Weintraub, 2001). SLPs will refer to the manual for explicit instructions regarding administration and scoring procedures. Administration time will range between 5-20 minutes.
3. Administer Subtest 6 from the *Apraxia Battery for Adults-Second Edition* (ABA-2):
 - o Subtest 6 (Inventory of Articulation Characteristics) of the ABA-2 is a rating scale, in which speech characteristics are evaluated on 15 different items (e.g., the patient exhibits: marked difficulty initiating speech; highly inconsistent errors; or visible/audible searching). The range of scores on Subtest 6 is 0-15, where a score above 5 is thought to signify the presence of apraxia of speech, an impairment in the programming of movements for the purpose of speaking without neuromuscular deficit (Dabul, 2000). Higher scores indicate more severe apraxia of speech. SLPs will refer to the manual for explicit instructions regarding administration and scoring procedures. Administration time will range between 10-15 minutes.
4. Administer the *Pyramids and Palm Trees Test* (PPTT)
 - o The PPTT is a test of semantic processing. This test assesses the degree to which a patient can access meaning from pictures and words. Information from

the test will help determine whether a patient's difficulty in naming or pointing to a named picture is due to a difficulty in retrieving semantic information from pictures, or a difficulty in retrieving semantic information from words, or, in the case of a naming failure, a difficulty in retrieving the appropriate spoken form of the word (Howard & Patterson, 1992). SLPs will refer to the manual for explicit instructions regarding administration and scoring procedures. Administration time will range between 10-20 minutes.

5. Administer the *abstract reasoning sub-test of the WAIS*
 - This test is a measure of nonverbal reasoning. The WAIS sub-test was constructed to test whether individuals are able to reason by analogy and adopt this way of thinking as a consistent method of inference. SLPs will refer to the manual for explicit instructions regarding administration and scoring procedures. Administration time will range between 15-20 minutes.

